The present application is for the development and evaluation of two VR simulations (interactive VR, 360° video) applied to the context of Emergency Medicine. The aim of this pilot study is to develop two VR simulations, and to compare their effectiveness with traditional theatre-based simulations. Given the novelty of both interactive VR and 360° video simulations, our primary objective is to compare knowledge retention and application of knowledge during a paper quiz and traditional theatre-based emergency department simulations following preparation with either 360° video training or interactive VR training. The secondary objectives are to assess the usability and feasibility (resources), as well as the emotional engagement, of the above three modalities.

Methods:

Phase 1: Creation of Content: A software engineer with expertise in video-game development will be hired to develop the computer-generated emergency department in collaboration with the educators and clinicians on the team. A theatre-based trauma scenario from the current uOttawa Emergency Department curriculum will be adapted to the **VR platform**. This virtual environment will allow a team of students to manage a patient simultaneously through their avatars, from a first-person perspective. In parallel, a well-managed depiction of the same scenario will be scripted and recorded using a **360-degree HD video** camera. The recording will be made using the investigators as actors, with additional interprofessional volunteers recruited as needed. These videos will be edited and then converted to an application that can be uploaded to the Oculus® platform. Both platforms will undergo piloting for content and usability. The amount of time, money and other resources required to develop each of these scenarios will be calculated.

Phase 2: Evaluating the intervention:

Participants: 40 residents and medical students will be recruited to participate in the evaluation of the VR modules. Participants will be randomized to one of two groups (20 participants per group) – interactive VR or 360° video education. See Figure 1.

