Pre-Test: Prior to participating in one of the two educational interventions (360°-video or interactive VR), participants will complete a pre-test of their content-specific knowledge and knowledge application with respect to basic presentations to the emergency department. All participants will complete a video-recorded simulation of an emergency department case, half will complete Case A while the remaining half will complete Case B. These cases will be counter-balanced at post-test in order to account for any possible differences in case difficulty. All participants will also complete a knowledge test which will consist of approximately 20 multiple-choice questions with a mark out of 20 for a minimum score of 0 and maximum score of 20. Questions will be based on Advanced Cardiac Life Support (ACLS) guidelines and algorithms. Team performance will be recorded for subsequent scoring (see measures and analysis section below). During the traditional theatre-based simulation sessions, we will measure the learners' HR and HRV with the use of a Polar H10™ chest belt linked with a commercial capture and analysis software (EliteHRV™) program on an iPad. This will allow us to measure both arousal and stress responses, as physiological indication of the learners' emotional engagement.

Intervention: Following the pre-test, participants will either participate in the interactive VR or the 360° educational video. In each condition, the scenarios will be matched for duration, and will be followed by a debriefing session focused on the learners' comprehension of the case, their rationales for decisions, as well as closing any observed gaps in performance. UOSSC-affiliated instructors with formalized simulation and debriefing training will lead the debriefing. The learners' HR and HRV will be captured during the simulation and the debriefing sessions as a measure of engagement during the activity.

Post-Test: Two weeks after the education session, all participants will complete a post-test of their knowledge and knowledge application (matched in difficulty with pre-test), as well as lead a theatre-based simulated case. Participants who completed Case A will now complete Case B and vice versa. The sessions will be videotaped for subsequent rating of clinical and team performance. We will also capture their HR and HRV again as measures of physiological arousal and stress.

Measures and Analyses:

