This will be an equivalency study which hypothesizes that there will not be a difference in learning between 360-VR or interactive VR. The primary outcome measures for this study will be changes in knowledge and in clinical performance from pre-test to post-test. Two experienced simulation instructors will view and score the videos, blinded to the group allocation and whether the scenario is pre or post the intervention. The raters will evaluate the learners using the Ottawa GRS scale as well as a checklist of expected actions for the scenario. The raters will independently rate the videos, and their level of agreement will be calculated using an intra-class correlations coefficient. The averaged scores, as well as scores on the knowledge tests, will be submitted to separate mixed-design analyses of variance (ANOVA) with time (pre, post) as a repeated-measure and groups (interactive VR, 360° video) as a between-subject variable. Post-hoc analyses will be conducted with relevant paired or unpaired t-tests.

The secondary outcomes measures are arousal and stress responses during pre and post theatre-based simulation sessions, educational sessions, and debriefing sessions. Mean and peak HR and HRV (rMSSD, pNN50) will be submitted to separate ANOVAs, with time (pre-test, debriefing, post-test) as a repeated measure and group (interactive VR, 360° video, theatre-based) as a between-subject variable. Post-hoc analyses will be conducted with relevant paired/unpaired t-tests.

Another secondary outcome measure will be the cost-effectiveness of the education interventions, based on Levin’s cost effectiveness model⁴ applied to simulation-based education⁵. The cost categories will include equipment and materials (e.g. market price of equipment, maintenance cost), personnel costs (e.g. staff salary, volunteer time), facility costs (e.g. facility rental fee, facility maintenance), required client inputs (e.g. learner costs, opportunity costs), and other program costs (e.g. communications fees, servers for storage and retrieval of information). These will be summed into a dollar estimation for each modality, and compared using a one-way between-subject ANOVA, with group (interactive VR, 360° video) as the between variable.

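### Training level (resident or student) is named neither in the allocation nor in the primary ANOVA; this costs precision only where gains differ by level, and it is nearly free to fix

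*Protocol*

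**What the plan says.** Under Methods, Phase 2 (Participants), the protocol recruits a mixed sample: "40 residents and medical students will be recruited to participate in the evaluation of the VR modules". The split between residents and students is not given. On allocation it says only this: "Participants will be randomized to one of two groups (20 participants per group"), one group for each virtual-reality method. It names no stratification factor, block size or randomisation method.

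Under Measures and Analyses, the aim is equivalence: "This will be an equivalency study which hypothesizes that there will not be a difference in learning between 360-VR or interactive VR". The outcomes are defined as change: "The primary outcome measures for this study will be changes in knowledge and in clinical performance from pre-test to post-test". The analysis consists of "separate mixed-design analyses of variance (ANOVA) with time (pre, post) as a repeated-measure" and "groups (interactive VR, 360° video) as a between-subject variable". Training level is neither a factor nor a covariate. The follow-up tests are loosely specified: "Post-hoc analyses will be conducted with relevant paired or unpaired t-tests".

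The Pre-Test paragraph gives the knowledge quiz "a mark out of 20 for a minimum score of 0 and maximum score of 20", based on ACLS guidelines. It also counterbalances Cases A and B so that case difficulty does not disturb the results. No comparable protection is stated for training level.

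**The concern.** Residents and medical students can be expected to differ in ACLS knowledge and in leading an emergency case. They may also differ in how much they gain: a resident who starts near 20 on the quiz has less room to improve than a student.

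With 20 per arm, an unstratified allocation will often leave the arms with unequal shares of residents. If gains differ by level, that imbalance moves the estimated difference between the two methods in a given trial, and over repeated trials it widens the standard error. A trial that wants to show a small difference between arms should not carry avoidable width. Stratified allocation has to be set before participants are randomised, so the protocol is the natural place for it.

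**Working it through.** **The plan's own figure.** 2 x 20 = 40 agrees with the stated total. The protocol gives no alpha, power, SD or equivalence margin, so the sample size cannot be derived further.

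**Inputs.** From the protocol: 40 participants, 20 per arm, two time points, outcomes defined as change. Assumed, because not given: 10, 20 or 30 residents among the 40; fixed 20:20 allocation without stratification; within-level SD of 1 at each time; pre-post correlation r = 0.5. Let g be the resident-minus-student difference in the analysed quantity, in within-level SDs.

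**Step 1: what the primary test sees.** With two arms and two times, the group-by-time test is a t-test on change scores. If the level effect is a at pre-test and b at post-test, the level effect on change is b - a. When a = b it is zero, so g = 0 however large the difference in ability. The within-level variance of change is 2(1 - r) = 1 at r = 0.5, so g is simply b - a in score SDs.

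**Step 2: chance imbalance.** The number of residents in one arm is hypergeometric. With 20 residents of 40:
- P(10 v 10) = C(20,10)²/C(40,20) = 0.248; P(11 v 9, either way) = 2 x 0.205 = 0.409.
- P(differ by at least 4) = 1 - 0.248 - 0.409 = 0.343.
- P(12 v 8, either way) = 0.230, so P(differ by at least 6) = 0.343 - 0.230 = 0.113.

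With 10 or 30 residents, an imbalance of 20 percentage points or more has probability 0.273, and of 30 points or more 0.065.

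**Step 3: shift in one trial.** Shift = imbalance in resident share x g. A 12 v 8 split is 0.60 - 0.40 = 0.20, so the shift is 0 at g = 0, 0.1 SD at g = 0.5 and 0.2 SD at g = 1.

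**Step 4: precision.** With resident share p, the unadjusted standard error is larger by the factor sqrt(1 + p(1 - p)g²). The last column comes from 6,000 simulated trials per setting (20 residents, level effect 1 SD at pre-test) and gives the SD of the estimated arm difference in change.

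| Gap in gain g | Factor, p = 0.5 | Factor, p = 0.25 | Simulated SD: unadjusted / level-adjusted |
|---|---|---|---|
| 0 | 1.000 | 1.000 | 0.316 / 0.319 |
| 0.5 | 1.031 | 1.023 | 0.328 / 0.324 (ratio 1.01) |
| 1 | 1.118 | 1.090 | 0.354 / 0.320 (ratio 1.11) |

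The simulated ratios are slightly below the formula because adjusting for level has a small cost of its own. The mean error was about 0 in every setting.

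For scale, the 90% interval half-width at 20 per arm is t(0.95, 38) x sqrt(2/20) = 0.533 SD. It becomes 0.533 x 1.031 = 0.55 at g = 0.5 and 0.533 x 1.118 = 0.60 at g = 1.

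**Step 5: the shift and the wider error are one effect.** The SD of the imbalance in resident share is 0.160 (p = 0.5). At g = 1 it adds 0.160 to a within-level standard error of sqrt(2/20) = 0.316: sqrt(0.316² + 0.160²) = 0.354, the unadjusted value in the table.

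**Step 6: comparisons not corrected for baseline.** For an unpaired comparison of post-test scores, a stable 1 SD gap does not cancel. The simulated SD is 0.351 against 0.319 with no level effect, about 10% larger. The group main effect averages pre-test and post-test and is exposed in the same way.

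**Step 7: what covariates recover.** In a 12 v 8 split the correlation between level and arm is 0.20. Adjusting for level removes the shift at a variance cost of 1/(1 - 0.20²) = 1.042, about 2% in standard error. Modelling the post-test score on pre-test score and level leaves residual variance 1 - r² = 0.75. The standard error is then sqrt(0.75 x 2/20) = 0.274, or about 0.28 after the small cost of estimating the covariates, against 0.32 to 0.35 for unadjusted change. Most of that gain comes from the pre-test covariate.

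**The case against.** The strongest reply is that the mechanism hardly reaches the primary analysis. Change is the outcome, so any stable difference in ability drops out, and nothing in the protocol shows that gains differ by level, still less by 1 SD. The ceiling argument concerns the quiz, not the rated simulation performance. This reply stands, and it limits the size of the point.

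A reader might infer more than the documents support in four ways.

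- *That the protocol decided against stratification.* It does not describe the allocation method at all. It is silent, and the detail may sit in a document not at hand.
- *That an imbalance biases the comparison.* Under randomisation the expected error is zero, and the unadjusted interval already carries this variation.
- *That the shift and the loss of precision are two harms.* Step 5 shows that they are the same variance seen in one trial and over many.
- *That nothing can be done after allocation.* Covariate adjustment recovers nearly all of it, at about 2% of the standard error even in a 12 v 8 split, and an analysis plan could add the covariates.

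It is also fair to say that the Background calls this a pilot and that no margin is stated, so a shift of 0.1 to 0.2 SD cannot be shown to change a conclusion.

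What remains is that the protocol does fix a model, with time and group only. Its post-hoc wording permits unpaired comparisons that a stable level difference does affect. A plausible source of differing gains is left unprotected when protection costs almost nothing.

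**Conclusion.** The point holds in a limited form. The sample mixes two training levels, no stratification by level is named, and level is absent from the stated primary model. For the primary change outcomes the loss depends entirely on a difference in gain: about 0% in standard error with equal gains, 1-3% with a 0.5 SD gap, and 11-12% with a 1 SD gap. For unpaired post-test comparisons, a stable 1 SD gap alone costs about 10%.

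These figures assume 20 residents of 40, unstratified 20:20 allocation and a pre-post correlation of 0.5, none of which the protocol gives. With 10 or 30 residents, the chance of a 20-point imbalance falls from 34% to 27%, and the formula's loss at a 1 SD gap falls from 12% to 9%. The effect is chance error, not systematic bias. This is a minor to moderate improvement and does not threaten the trial's validity.

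**What to change.** State in the protocol that allocation is stratified by training level (resident, medical student), with blocks within each stratum. Replace the time-by-group ANOVA for each primary outcome with a model of the post-test score on group, pre-test score and training level. Level should enter together with the pre-test score: when the pre-test slope is below 1, part of a stable level difference no longer cancels. Any follow-up comparison of the arms should come from the same model, not from an unpaired test of raw post-test scores.

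If allocation is already complete, prespecify training level and pre-test score as covariates before the outcome data are examined.

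The cost is a second allocation list and one degree of freedom for each covariate. No further participants are needed, and the only data used beyond the planned scores is each participant's training level.

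### The Case A/B split is not tied to randomised arm and the ANOVA has no case-order term, so counter-balancing is not guaranteed to clear case difficulty from the clinical-performance comparison

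*Protocol*

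**What the plan says.** The relevant statements stand in four parts of the protocol's Methods, Phase 2.

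- **Participants.** The sample is 40, and "Participants will be randomized to one of two groups (20 participants per group"). Case order is not mentioned.
- **Pre-Test.** Everyone leads one recorded simulation: "half will complete Case A while the remaining half will complete Case B". The purpose is given as "These cases will be counter-balanced at post-test in order to account for any possible differences in case difficulty".
- **Post-Test.** "Participants who completed Case A will now complete Case B and vice versa". Each learner therefore does both cases, one at each time.
- **Measures and Analyses.** The primary outcomes are "changes in knowledge and in clinical performance from pre-test to post-test". The scores go into separate mixed ANOVAs "with time (pre, post) as a repeated-measure and groups (interactive VR, 360° video) as a between-subject variable". Neither case nor case order is a factor. The study is framed as one of equivalence between the two arms.

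The protocol does not say whether the two halves are formed within each arm, how case order is assigned, or whether allocation to arm comes before or after the pre-test.

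**The concern.** Each learner meets a different case at each time, so any difference in difficulty goes straight into that learner's change score, with one sign for those who start with Case A and the opposite sign for those who start with Case B. It cancels from the comparison of arms only when the Case-A-first share is the same in both. Splitting the 40 learners 20/20 overall does not secure that, and a model with only time and group cannot repair it afterwards.

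The contrast at stake is the group-by-time term for clinical performance, one of the two primary outcomes. With 20 learners per arm, a chance imbalance in case order could imitate or mask a difference between the modalities, and the added noise makes it harder to show that they are equivalent. The investigators evidently thought case difficulty mattered, since they built a counter-balance to deal with it.

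**Working it through.** The protocol gives no figure for this point, so there is nothing of its own to reproduce.

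**Inputs from the protocol.** 40 participants, 20 per arm; 20 start with Case A and 20 with Case B; all swap at post-test; ANOVA on time and group only.

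**Assumptions, not in the protocol.** (a) Case order is assigned at random, independently of arm, with 20/20 totals. (b) d, the mean score on Case A minus that on Case B, is 0.25, 0.5 or 1 SD of the change score, where the SD is taken within case order and set to 1.

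**Step 1: effect on the contrast.** Let τ be the true mean change. A Case-A-first learner's change has mean τ − d and a Case-B-first learner's has mean τ + d. An arm with Case-A-first share p has mean change τ + d(1 − 2p). The difference between arms is therefore shifted by −2d(p₁ − p₂). If one arm has k Case-A-first learners out of 20, the other has 20 − k. The size of the shift is then 2d × |k − (20 − k)|/20 = 2d × |k/10 − 1|.

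**Step 2: how often imbalance occurs.** Under (a), k is hypergeometric (40, 20, 20), with SD √(20 × 0.5 × 0.5 × 20/39) = 1.60.

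| Split in the two arms | Probability of this or worse | Shift at this split |
|---|---|---|
| 11/9 vs 9/11 | 75.2% | 0.2d |
| 12/8 vs 8/12 | 34.3% | 0.4d |
| 13/7 vs 7/13 | 11.3% | 0.6d |
| 14/6 vs 6/14 | 2.6% | 0.8d |

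Exact 10/10 in both arms has probability 24.8%. The shift has mean 0, mean absolute size 0.25d and SD 4 × 1.60/20 = 0.32d.

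**Step 3: cost in precision.** With balance, the true standard error of the contrast is √(2/20) = 0.316. With random order it is √(0.1 + (0.32d)²). The simulated values below (40,000 runs, t-test on change scores, two-sided 5%) agree with this formula to within 0.001.

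| d (SD) | True SE, random order | True SE, balanced | Type I error, random order | Type I error given a realised 13/7 |
|---|---|---|---|---|
| 0.25 | 0.326 | 0.316 | 5.0% | 6.5% |
| 0.5 | 0.354 | 0.316 | 5.0% | 10.5% |
| 1 | 0.451 | 0.316 | 5.0% | 18.9% |

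From the squared ratio of the standard errors, the loss of effective sample size is about 6%, 20% and 51%.

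**Step 4: what balance alone achieves.** With 10/10 in each arm, p₁ = p₂ and the shift is exactly 0 for any d. If the model still omits case order, however, the ±d in the change scores stays in the residual. The reported standard error is then too large and the test is conservative: simulated type I error is 4.1%, 2.7% and 0.5% at d = 0.25, 0.5 and 1 SD. The gain from balance reaches the reported result only if case order is also in the model.

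**The case against.** The strongest reply is that the protocol does not describe an unbalanced design. Its wording is met equally well by 10/10 in each arm, which is what many readers would understand by counter-balancing. The Participants section also points to Figure 1, of which only text labels could be read; these say only that the simulation is A or B. This stands: the protocol is silent on the split within arms, and it cannot be said to make the split without regard to arm.

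A reader might also infer that case difficulty biases the primary comparison. The protocol does not support that. Under independent random order the shift averages zero and the type I error is 5.0% at every d tried, so this is ordinary chance imbalance. In about 66% of allocations the split is 11/9 or better, a shift of at most 0.2d. Systematic bias would need case order to be assigned non-randomly and in line with arm, and nothing in the protocol says so. The raised error rates after a realised 13/7 split describe an unlucky allocation, not the design as a whole.

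Three further points are fair. An overall 20/20 split does remove case difficulty exactly from the pooled pre-to-post effect, because the overall Case-A-first share is one half. The knowledge test, the other primary outcome, does not use the cases. And a case-order term alone would remove the shift even at 13/7, where the correlation of arm with order is 0.3, for a variance factor of 1/(1 − 0.3²) = 1.10, or about 5% in the standard error.

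It might also be said that such detail belongs in a randomisation or analysis plan. For the model term that is arguable. It does not hold for the assignment rule: an analysis plan cannot create balanced cells after the learners have done their cases, and the protocol already states both a rule and its purpose.

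**Conclusion.** The point holds in a limited form. The assignment rule as written, together with an ANOVA on time and group only, does not guarantee that case difficulty is removed from the clinical-performance group-by-time contrast. If case order is random and independent of arm, the consequence is lost precision and exposure to chance imbalance: a true standard error about 3%, 12% and 43% larger than under balance (0.326, 0.354 and 0.451 over 0.316) for d of 0.25, 0.5 and 1 SD. Those values of d are assumptions. If the two cases are close in difficulty, the cost is small, and if each arm was always meant to be split 10/10, the allocation part is only a matter of wording. This is an improvement available at almost no cost, not a demonstrated error.

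**What to change.** 1. Randomise from one blocked list to four cells of 10: interactive VR with Case A first, interactive VR with Case B first, 360° video with Case A first, 360° video with Case B first. If the pre-test comes before allocation, assign case order first and use it as the stratum for blocked randomisation to arm.
2. Reword the Pre-Test text to say: within each group, half will complete Case A first and half Case B first.
3. In Measures and Analyses, add case order as a between-subject factor to the clinical-performance ANOVA, together with its interaction with time, because that interaction carries case difficulty. In an analysis of change scores, case order as a covariate does the same. The knowledge-test ANOVA needs no change.

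The cost is a different randomisation list, two small edits to the text and one or two residual degrees of freedom. No additional participants or assessments are needed. If recruitment has already begun, step 3 can still be taken for the whole sample, and the remaining learners can be assigned so as to bring each arm close to 10/10.

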Imagine a virtual classroom - learners wearing VR headsets in the safety of their home are immersed in a computer-generated simulation centre. Through their avatars, they can interact from a first-person perspective with their environment, colleagues and instructors. The virtual patient has been in a car accident and the learners, by interacting with the virtual trauma bay environment, must work together to perform a primary trauma survey and resuscitate the patient. The **interactive VR** environment provides the team with real time information in a realistic environment that includes the uncertainty, noise, and time pressures of a real case. At several key points in the VR video, learners are presented with interactive decision points, and their choices determine how the rest of the video unfolds

Alternatively, imagine a second immersive environment based on high-definition **360° video** obtained from our simulation centre. Single learners, wearing a VR headset, find themselves in the resuscitation room, at the foot of the bed, leading a trauma team through the assessment and resuscitation of a patient in a virtual scenario. An example of a non-interactive VR video developed by our team for the obstetrical curriculum can be found at (<https://youtu.be/AqdwMHPe0BY>).

In both the interactive VR and 360° video experiences as well as the pre- and post-test traditional theatre-based simulations, our study will aim to measure participants' heart rate (HR), heart rate variability (HRV) and oxygen saturation levels as markers of arousal and stress responses. These will serve as a physiological indication for: 1) their comfort and change in comfort when leading scenarios and making decisions for critically ill patients in real-time and 2) their emotional engagement in their own learning throughout the immersive experiences.

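### Both arms train on a trauma scenario, but the primary knowledge quiz is based on ACLS, and the protocol does not reconcile the two

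*Protocol*

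**What the plan says.** **Training.** Phase 1: Creation of Content states: "A theatre-based trauma scenario from the current uOttawa Emergency Department curriculum will be adapted to the" VR platform. For the other arm, "a well-managed depiction of the same scenario will be scripted and recorded using a" 360-degree camera. The Budget Justification again calls the interactive product a trauma bay scenario. The Background illustrates it with a car-accident victim, where learners "must work together to perform a primary trauma survey and resuscitate the patient". The Intervention paragraph adds a debriefing on learners' "comprehension of the case, their rationales for decisions, as well as closing any observed gaps in performance".

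**Quiz.** The Pre-Test paragraph describes about 20 multiple-choice questions scored 0 to 20 and says: "Questions will be based on Advanced Cardiac Life Support (ACLS) guidelines and algorithms". ACLS is named nowhere else in the protocol. The Post-Test paragraph matches the second test to the first in difficulty.

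**Role of the quiz.** Measures and Analyses makes change in knowledge and change in clinical performance the primary outcome measures. It hypothesises no difference in learning between the arms and plans a mixed ANOVA of time by group. There are 20 participants per group.

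**The concern.** A knowledge test can separate two teaching methods only on material that the methods teach. The training is described as trauma and the test as ACLS. Followed as written, the plan could score learners partly on content that neither arm was taught.

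The direction matters because of the hypothesis. In a superiority trial an insensitive outcome works against the claim. Here it works for it: items that carry no arm difference pull the total score towards the hypothesised result. The protocol's Outcome section says the data will help decide which modality is best suited to distanced simulation, so a diluted comparison on a primary outcome would bear on that choice.

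**Working it through.** **Step 1. Does any wording link the quiz to the training?**

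- The primary objective, just before Methods, is to compare retention and application of knowledge on a paper quiz and in theatre simulations after preparation with either modality. This shows an intended link but names no content.
- The Pre-Test paragraph says "participants will complete a pre-test of their content-specific knowledge and knowledge application with respect to basic presentations to the emergency department". Calling the knowledge content-specific again shows intent, but the content named is basic emergency presentations, not the training scenario.
- In Phase 1, "Both platforms will undergo piloting for content and usability". That covers the platforms, not the quiz.
- The debriefing concerns the case; ACLS is not mentioned.
- The post-test is matched to the pre-test on difficulty; matching to taught content is not stated.

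The link is intended, but nothing reconciles ACLS with trauma.

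**Step 2. Dilution formula.** The protocol gives no effect size, SD, margin or power, so there is no planned figure to reproduce. Let D be the expected arm difference in marks if all 20 items are taught. If k items are untaught and carry no arm difference, the expected difference is D × (20 − k)/20. If D = 0 it stays 0.

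**Step 3. Illustration.** From the protocol: 20 items and 20 per arm. Assumed: 55% correct at pre-test; taught items 70% versus 85% correct at post-test; untaught items stay at 55%; two-sided 5%. Then D = 20 × (0.85 − 0.70) = 3 marks. The variance of change at full alignment is 20 × 0.55 × 0.45 + 20 × 0.70 × 0.30 = 9.15 in one arm and 4.95 + 20 × 0.85 × 0.15 = 7.50 in the other, an average SD of about 2.9.

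The test is a t-test on change scores, equivalent to the time-by-group term of the planned ANOVA. There were 20,000 simulated trials per setting. The last column repeats the exercise with taught items at 70% versus 80% (D = 2).

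| Untaught items | Difference (70% v 85%) | Detected | Detected (70% v 80%) |
|---|---|---|---|
| 0 | 3.0 | 89% | 55% |
| 5 | 2.25 | 65% | 34% |
| 10 | 1.5 | 34% | 17% |
| 15 | 0.75 | 12% | 8% |

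Between-learner variation (SD 0.5 or 1.0 on the logit scale) moves the fully aligned figures to 84–88% and 49–54%, and leaves those at 10 untaught items at about 34% and 17%.

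**Step 4. Cross-check.** Normal approximation with an assumed SD of 3: SE = 3 × √(2/20) = 0.949 and power = Φ(difference/SE − 1.96). For 3, 2.25, 1.5 and 0.75 marks this gives 89%, 66%, 35% and 12%. With SD 2 the figures are 99.7%, 95%, 66% and 22%; with SD 4, 66%, 43%, 22% and 9%.

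**Step 5. Equivalence reading.** The protocol states no margin. Assume 2 marks, a true aligned difference of 2 marks and two one-sided 5% tests (normal approximation). Equivalence is then declared in 5%, 20%, 47% and 76% of trials with 0, 5, 10 and 15 untaught items if the SD is 2. If the SD is 3, the figures are 4.5%, 11%, 21% and 31%.

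**Step 6. Would the pre-to-post gain give a warning?** With 10 untaught items and taught items at 70% versus 85%, the arm gains are 10 × 0.15 = 1.5 and 10 × 0.30 = 3.0, an average of 2.25 marks. Its SE is about 3/√40 = 0.47, so it is nearly always significant: the lowest value over all runs was 0.966. With 15 untaught items the average gain is 1.125 marks, and the gain is significant in only about 46–61% of trials across the settings.

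**The case against.** The strongest reply is that no contradiction is shown. One passage names the setting of the scenario and the other the source of the quiz items, and both can be true. The scenario includes resuscitation, and the protocol defines neither the scope of ACLS nor the scenario script, so the overlap cannot be settled from the text. The trauma wording sits in the content-development and budget text; the evaluation phase speaks only of emergency presentations, and the Budget Justification calls the scenario adaptable to other clinical content. If the trauma wording is out of date, only a text correction remains. This stands as far as it goes: a mismatch is not proven. It does not remove the problem, because Phase 1 is the operative description of what is built for both arms, and nothing says that other content replaced it.

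A reader might infer that the quiz has no connection with the teaching. The primary objective and the Pre-Test wording do not support that; they show an intended link.

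A reader might also infer that the clinical performance outcome shares the fault. The protocol says only "All participants will complete a video-recorded simulation of an emergency department case", with Cases A and B. That inference would rest on silence, so it is not part of this point.

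Finally, every effect size above is assumed, and the Background says there is no evidence that either method is superior. If the arms are truly equal, dilution does no harm. With the smaller assumed difference, detection is only about 55% even with a perfectly aligned quiz; that shortfall comes from 20 per arm, which is a separate matter.

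**Conclusion.** The point holds as a stated, unreconciled inconsistency on a primary outcome, with a known direction of risk and an unknown size. It should be corrected. It does not show that the quiz is invalid or that the trial will wrongly conclude equivalence.

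The direction rests on two conditions: that the arms truly differ on taught content, and that untaught items carry no arm difference. Given those, the shrinkage to (20 − k)/20 is exact. The fall in detection from about 89% to about 34% with half the items untaught is illustration only, since the overlap, the item probabilities and the arm difference are not in the protocol. A significant gain over time should not be read as proof of alignment, since about 97% or more of simulated trials show one with 10 items untaught. Severe misalignment would often show as an absent gain.

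**What to change.** Before data collection, reconcile the Phase 1, Pre-Test and Budget Justification text in one of two ways:

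- If the training is the trauma scenario, write both quiz forms from that scenario's learning objectives and replace the ACLS sentence accordingly.
- If the training is in fact ACLS-based, correct the trauma description and keep the quiz.

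The first option means rewriting some multiple-choice items and keeping the two forms matched in difficulty, as the protocol already requires. The second is a text correction. Neither needs more participants, procedures or analyses.
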